### b. Cognitive Function Assessments

Cognitive tasks. A valid cognitive battery (NIH Toolbox) will be used in this study to assess various aspects of cognitive performance including executive functioning, memory, language, and processing speed.

c. Self-Reported Function and Quality of Life. The Activity Measure for Post-Acute Care (AM-PAC) will be used to assess participants' level of perceived functioning. The total score on the AM-PAC is an excellent composite measure of disability or difficulty in performing basic and instrumental ADLs, especially those related to lower extremity function, and inability to move around (mobility limitations) which contribute the most to dependency, need for assistance from another person or a device, placement in an assisted care facility or a nursing home. It examines a set of functional activities that are likely to be encountered by most adults during daily routines during inpatient care, with outpatient post-acute services, or in the community

setting outside rehabilitation. Because functional activity is multidimensional, AM-PAC assesses multiple aspects (i.e., difficulty, assistance, limitations) of an individual's ability to perform specific daily activities in three functional areas: Basic Mobility (131 items), Daily Activity (88 items), and Applied Cognitive (50 items). AM-PAC is administered on a computer using software licensed by PAC-Metrix.

The Medical Outcomes Study Short-Form Health Survey (SF-36) will be used to provide a psychometrically valid measure of health-related quality of life (HRQOL). The SF-36 comprises a single multi-item self-report questionnaire that assesses 8 health concepts, yielding an overall score and individual scores for the eight subscales. Subscales assessing limitations in physical activities; limitations in usual role activities due to physical problems; bodily pain; vitality (energy and fatigue); and general health perceptions are particularly relevant to this study. The SF-36 has been utilized in many studies of HRQOL associated with a variety of medical conditions and it has often been used to measure changes in HRQOL associated with a variety of treatment interventions.

e. Pain Assessments. The Brief Pain Inventory (BPI) will be used to assess the presence and location of daily pains, as well as pain severity and pain-related interference. The BPI measures pain severity using a series of 0 (no pain) to 10 (worst possible pain) scales, which assess average pain, worst pain, and least pain in the past week, as well as current pain at the time of testing. There are seven BPI interference questions, each ranging from 0 (does not interfere) to 10 (completely interferes), assessing the extent to which pain has interfered over the past 24 hours with general activity, mood, walking ability, normal work, relations with other people, sleep, and enjoyment of life. This instrument has been validated for assessing outcomes in participants with non-cancer pain and has been used to quantify treatment outcomes.

f. Systemic Inflammatory biomarkers. Standard inflammatory biomarkers (i.e., IL-6, TNFa, and novel markers of inflammation) will be measured by ELISA at Baseline and the 3-month visit. All samples will be measured in duplicate and the average of the two measures will be used for data analyses.

g. Other measures

Dietary Fat (Block) questionnaire. Poor absorption of curcumin has been reported for various preparations, with enhanced absorption in high fat diets. This brief (13 item) "fat screen" identifies individuals with "high" fat intake, a potential confounder due to enhanced curcumin absorption.

Self-reported physical activity. The Rapid Assessment of Physical Activity (RAPA) is a 9-item questionnaire developed to assess strength, flexibility, and level and intensity of physical activity among older adults.

Safety. As a safety check to ensure no adverse biological changes have occurred, the following measures will be completed at screening, baseline, and each monthly visit:

- Study Coordinator will review any changes in medication, ED visits or hospitalizations, or side effects since previous visit with the participant
- At monthly visits, 30 cc of blood will be drawn and analyzed for a CHEM-15 metabolic profile (Albumin, Albumin/Globulin Ratio (calculated), Alkaline Phosphatase, ALT, AST,

BUN/Creatinine Ratio (calculated), Calcium, Carbon Dioxide, Chloride, Creatinine with GFR Estimated, Globulin (calculated), Glucose, Potassium, Sodium, Total Bilirubin, Total Protein, Urea Nitrogen) as well as for a complete blood count (WBC, RBC, Hemoglobin, Hematocrit, MCV, MCH, MCHC, RDW, Platelet Count, MPV and Differential (Absolute and Percent - Neutrophils, Lymphocytes, Monocytes, Eosinophils, and Basophils).

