### Specific Aims:

Specific Aim 1 - To examine the effects of dietary supplementation with curcumin on changes in physical function (walking speed, muscle fatigue, and grip strength) and in

self-reported physical activity

*Hypothesis 1 – Dietary supplementation with curcumin will maintain or improve walking speed, muscle fatigue, strength, and physical activity compared to controls.*

*Specific Aim 2 – To examine the effects of dietary supplementation with curcumin on cognitive performance (attention, memory), and pain symptoms.*

*Hypothesis 2 - Dietary supplementation with curcumin will maintain or improve attention and memory and reduce pain symptoms.*

*Specific Aim 3 – To examine the effects of dietary supplementation with curcumin on markers of systemic inflammation*

*Hypothesis 3 - Dietary supplementation with curcumin will decrease levels of IL-6 and of other systemic and cellular biomarkers of inflammation*

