### Study Population

The RCT will include 24 moderately functioning, sedentary adults age 70 years or older with elevated levels of systemic inflammation but without overt disease conditions. We estimate that up to 324 potential participants will undergo screening procedures to identify 24 persons eligible for enrollment in the RCT.

Based on our previous studies, we anticipate that the average age of participants will be approximately 77.0 years, and that approximately 20% will be African Americans. In general, participants will have a relative low prevalence of comorbid diseases.

The key inclusion criteria are the following:

- (1) Age  $\geq 70$  years;
- (2) Mild to moderate physical impairment (Short Physical Performance Battery score  $\leq 10$ );
- (3) Sedentary lifestyle ( $< 120$  min per week of moderate intensity physical activity);
- (4) Chronic low-grade inflammation measured by IL-6  $> 2.5$  pg/ml. To minimize within person variability, IL-6 is the average of 2 measures taken 1-3 weeks apart at screening visits

See Table 1 for a complete list of eligibility criteria.

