### **In-Person Screening (Screening Visits 1 and 2)**

At Screening Visit 1, participants will be asked to give written informed consent for in-person screening tests and will then be evaluated for cardiovascular and other major diseases by a health review. The health review consists of a review of criteria in the telephone screen, medical and hospital admission history, medication inventory, and physical exam including blood pressure, pulse, weight, and waist circumference.

Short Physical Performance Battery (SPPB) will be performed and the Physical Activity Questionnaire will be administered.

Mini Mental Status Exam (MMSE) and Center for Epidemiological Studies – Depression Scale (CES-D) will be administered to identify potential participants with cognitive dysfunction or

clinically significant depression that would preclude participation. Participants will also provide a blood sample for additional eligibility requirements and participant safety measures.

Approximately 60 ml of blood will be drawn for laboratory tests to assure eligibility (complete metabolic panel, CBC with differential, serum ferritin, and IL-6).

Results of Screening Visit 1 will be reviewed by the PI or his designee. . At this time a copy of the Informed Consent document for the main study will be provided, to allow adequate opportunity for review and consideration before the baseline visit when consent for the main study is obtained. Ineligibles will be contacted by the Study Coordinator for an explanation of ineligibility and will receive a copy of abnormal laboratory results.

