### **Enrollment and Randomization**

24 eligible participants will be enrolled and randomized to allow for 6 participant failures or withdrawals

At the baseline visit, the Informed Consent document for the RCT will be reviewed with the potential participant and written consent obtained. Participants will undergo a battery of physical performance tests (400-meter walk; short physical performance battery, grip strength and endurance), formal tests of cognitive function, and a blood draw of about 60 ml (See Table 1). Quality of Life and pain will be assessed with the AM-PAC, the SF-36, and the Brief Pain Inventory (BPI). Self-report of physical activity and dietary fat intake will be obtained through brief questionnaires (RAPA and Block High Fat screen).

Participants will then be randomized to receive either curcumin (1000 mg/day; n = 15) or placebo (microcrystalline cellulose; n=15) for a three-month period. The study drug will be provided for the first month according to randomization.

Participants in both groups will be instructed to return to the research center every month for the duration of the three-month trial. At the monthly visits, compliance with the supplementation regimen for the previous month will be assessed by pill count and participants will be provided with another month's supply of study medication according to initial randomization. Participants will be queried about any adverse events they experienced since their previous visit and any medical history updates they may need to provide. Additionally, blood samples will be obtained (chemistry 15 panel and complete blood count) to ensure that no adverse changes have occurred since their previous visit.

To enhance retention and to ensure participant safety, participants will receive bi-weekly telephone calls throughout the intervention period to ascertain adverse events and express appreciation for participation.

Following the three month supplementation period (Month 3 visit), participants will complete a post-treatment assessment including the battery of physical performance tests (400-meter walk, short physical performance battery, grip strength and endurance); cognitive function tests; questionnaires for quality of life, pain symptoms, and physical activity; and a blood draw of approximately 60 ml (See Table 2).

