Approximately 3-4 weeks after the Month 3 visit (at Week 15 – 16), participants will receive a final telephone call to ascertain any late adverse events, discuss any abnormalities from the final safety lab results, and express appreciation for participation.

Table 2. Study Visit Schedule Visit Type	Phone screen (pre-screening)	Screening visit 1		Baseline visit	Week 2	1-Month Visit	Week 6	2-Month Visit	Week 10	3-Month visit	Week 15-16
	Basic eligibility screening	X	X								
Informed Consent (Screening)		X									
Health review and physical examination (including BP, pulse, weight, height, waist circumference)		X									
Medical History and Concomitant Medication		X									
Update Medical History and Concomitant Medication Info				X	X	X	X	X	X	X	
BP, pulse, height and weight, waist circumference		X		X	X	X	X	X	X	X	
MMSE, CES-D		X									
Physical Activity Questionnaire (RAPA)				X						X	
SPPB (including 4 m walk test)		X		X						X	
Phlebotomy		X		X	X	X	X	X	X	X	
IL-6		X								X	
Additional exploratory inflammatory markers (TBD)				X						X	
CBC and Comprehensive Metabolic Panel (CMP) (Safety blood tests)		X		X	X	X	X	X	X	X	
Informed Consent (Main Study), enrollment, and randomization				X							
400 m walk test				X						X	
Isokinetic dynamometry of knee flexors and extensors				X						X	
Isometric hand grip strength				X						X	
Cognitive Function Tests (NIH Toolbox)				X						X	
Quality of Life (AM-PAC, SF-36)				X						X	
Brief Pain Inventory				X						X	
Dietary Fat questionnaire (Block)				X							
Dispense study drug				X	X	X	X	X	X	X	
Scheduled phone call					X	X	X	X	X	X	X
Assess compliance, query adverse effects and events						X	X	X	X	X	X

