## **Statistical Analyses**

Sample size estimates for pilot studies are inherently difficult because by intent, a pilot study is meant to include a smaller sample than a fully powered study. The enrollment sample of 15 participants in the intervention group and 15 participants in the placebo group (allowing for at least 12 evaluable participants in each group after the expected 20% loss due to attrition) is intended to provide sufficient data to indicate feasibility of a larger study and to provide descriptive estimates of effects. Additionally, it will provide for nominal estimation (using a 95% confidence interval) of the mean changes in the inflammatory marker, IL-6, the primary outcome of this pilot.

Feasibility and acceptability of the proposed intervention in older adults will be evaluated by process variables including number of participants completing the study; medication compliance, number and severity of adverse events, and changes in Quality of Life attributable to study participation.

Efficacy will be assessed as effects of the intervention on functional performance (physical and cognitive measures; pain perception, and inflammatory processes (Specific Aims). The following outcomes will be evaluated: physical function (walking speed, muscle fatigue); cognitive function (attention, executive, and memory function); pain (self-report); and systemic inflammation (IL-6, CRP, TNF $\alpha$ , and novel markers)

For each outcome, we will take the value of that outcome after the 3-month supplementation period minus the value at baseline for each participant. Summary statistics and 95% confidence intervals will be provided for within group changes as well as between group differences.

Effect size of intervention on key outcomes for sample size calculations in the planning of a larger RCT. Based on a sample size of 15 per group and 20% attrition, we have 80% power to detect a between group difference of effect size 1.2. Specifically, if we use the root mean squared error from LIFE-P (adjusted for baseline log(IL-6) and treatment) of 0.52 for log(IL-6), then we can detect a mean difference of 0.62 (on the log scale) or equivalently the difference between 4.20 and 2.26 pg/ml (or a 46% difference). And for selection based on walking speed change, we used a within group standard deviation of 0.25, which leads to a detectable mean difference of 0.3 m/s.

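### The protocol text and the visit schedule disagree on when baseline IL-6, the primary outcome, is measured; a screening baseline would build regression to the mean into the within-group changes

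*Combined protocol and SAP*

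**What the plan says.** - **Outcome.** Statistical Analyses offers "nominal estimation (using a 95% confidence interval) of the mean changes in the inflammatory marker, IL-6, the primary outcome of this pilot". Change is the 3-month value minus the baseline value, and "Summary statistics and 95% confidence intervals will be provided for within group changes as well as between group differences".
- **Timing in the text.** Outcome Measures, item f, says that the inflammatory markers, IL-6 among them, "will be measured by ELISA at Baseline and the 3-month visit".
- **Timing in the schedule.** The IL-6 row of Table 2 has marks under Screening visit 1 and the 3-Month visit only. The row directly below it, "Additional exploratory inflammatory markers (TBD", is marked under Baseline and the 3-Month visit.
- **Use of IL-6 at screening.** In-Person Screening lists, for Screening Visit 1, "laboratory tests to assure eligibility (complete metabolic panel, CBC with differential, serum ferritin, and IL-6". Key inclusion criterion 4 (Study Population) requires a value above 2.5 pg/mL and says "IL-6 is the average of 2 measures taken 1-3 weeks apart at screening visits". Table 2 shows no mark for a second screening measure.
- **Blood at the Baseline visit.** Enrollment and Randomization includes "formal tests of cognitive function, and a blood draw of about 60 ml (See Table 1".
- **Hypothesis 3** (Specific Aims): "Dietary supplementation with curcumin will decrease levels of IL-6 and of other systemic and cellular biomarkers of inflammation". It names no comparator, whereas Hypothesis 1 compares with controls.

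**The concern.** Two parts of the plan give different answers on which pre-treatment sample supplies the primary outcome, and the analysis section does not settle it. Staff who work from Table 2 would run no IL-6 assay on the Baseline sample; staff who work from the outcome text would.

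The choice matters because screening IL-6 is the selection variable. People admitted because a measurement exceeded a cut-off will, on average, measure lower next time, treated or not. Averaging two screening measures weakens this but does not remove it. Both arms would then show a fall in IL-6 that is not a drug effect. The plan reports an interval for each arm's change, and Hypothesis 3 could be read as supported by a fall in the curcumin arm alone. Randomisation protects the between-group difference, so the stake is limited to the within-group results and to a primary outcome whose baseline is ambiguous.

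**Working it through.** **The plan's own figure.** 15 per group with 20% attrition leaves 15 × 0.8 = 12. A two-sided 5% two-sample t-test with 12 per group and effect size 1.2 has 80.2% power, so the stated 80% reproduces. Also 1.2 × 0.52 = 0.624, 4.20 × exp(−0.62) = 2.26, and 1 − 2.26/4.20 = 46%. This is a between-group figure and is not in dispute.

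**Inputs from the plan.** Residual SD of log IL-6 of 0.52, 12 evaluable per arm (both from Statistical Analyses), and an entry cut-off of 2.5 pg/mL (Study Population and Table 1; the Design section gives 2.0).

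**Assumptions not in the plan.** IL-6 is log-normal. The geometric mean before selection (GM) is 2.0 or 2.5 pg/mL. The correlation ρ between two log IL-6 values from one person is 0.5 to 0.8. Visit-to-visit errors are independent. There is no drug effect.

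**Step 1: total SD.** σ = 0.52/√(1 − ρ²), which gives 0.60, 0.65, 0.73 and 0.87 for ρ = 0.5, 0.6, 0.7 and 0.8.

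**Step 2: closed form for one qualifying value used as baseline.** Expected fall = σ(1 − ρ) φ(z)/(1 − Φ(z)), with z = (ln 2.5 − ln GM)/σ. For ρ = 0.7 and GM 2.0, z = 0.223/0.728 = 0.31 and φ(z)/(1 − Φ(z)) ≈ 1.00. The fall is 0.728 × 0.3 × 1.00 = 0.22 log units, and 1 − exp(−0.22) is about 20%. A simulation of the same case gave 0.220. The SD of change was 0.533, so the 95% half-width with 12 people is 2.201 × 0.533/√12 = 0.34.

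**Step 3: simulation of null arms.** 40,000 arms of 12 per scenario. A false decrease means that the whole t-based 95% interval for the within-group change lies below zero (nominal 2.5%). Ranges run over ρ = 0.5 to 0.8 and both geometric means.

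| Entry rule and baseline used | Spontaneous fall, log units (%) | False decrease, log scale | False decrease, raw scale |
|---|---|---|---|
| Entry on average of two; that average is baseline | 0.11–0.23 (10–20%) | 11–30% | 6–19% |
| Entry on average of two; Screening visit 1 value is baseline | 0.07–0.18 (7–16%) | 6–16% | 4–12% |
| One value for both entry and baseline | 0.14–0.31 (13–27%) | 13–44% | 7–30% |
| Separate Baseline-visit sample | 0.00 | 2.4–2.6% | not tabulated |

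In the first row, 0.04 to 0.05 of the log-scale fall arises only because the log of an average exceeds the average of logs. For example, at ρ = 0.5 and GM 2.0 the first two rows give 0.228 − 0.178 = 0.050. The raw-scale rates are free of this.

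**Step 4: between-group difference.** It averages 0.00 in every scenario, with two-sided type I error of 4.7 to 5.4%.

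**Step 5: wider assumptions.** With ρ of 0.5 to 0.9 and GM of 1.5 to 3.0 at cut-off 2.5, the closed-form fall is 8 to 35% for one measure and 4 to 23% for the mean of two log values. At cut-off 2.0 the ranges are 7 to 29% and 4 to 19%.

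**The case against.** - **Only one table cell dissents.** Table 2 was read from extracted text, one column header is blank, and several of its other rows have marks that fit poorly with the narrative. An artefact is possible. However, the IL-6 marks line up with the headers, the screening mark agrees with the In-Person Screening text, and the next row is marked at Baseline. The conflict stands on the text available.
- **The narrative already defines the baseline.** Baseline is a named visit, and item f of Outcome Measures says IL-6 is measured there. This is the more natural reading, and nothing says that the screening value is the analysis baseline. But the schedule contradicts it and the analysis section does not name the sample.
- **The harm is conditional.** It needs staff to follow Table 2 and readers to take a within-arm fall as efficacy in a placebo-controlled trial. The plan describes its estimates as descriptive, and its power statement is between-group. This limits the seriousness, but within-group intervals are still a planned output and the plan does not rank them below the between-group estimate.
- **The size rests on assumptions.** This is correct. At ρ = 0.9 and GM 2.0 to 3.0, the false-decrease rate is 7.6 to 9.1% (log) or 3.2 to 4.0% (raw) with the average as baseline, and 4.4 to 5.2% (log) or 2.2 to 2.7% (raw) with the Screening visit 1 value. The plan states no log transform for the change score, so the raw rates may be the relevant ones. The 44% figure needs single-value entry, which contradicts inclusion criterion 4.
- **A separate Baseline sample may not remove the whole effect.** If visit errors two weeks apart are correlated at 0.3 to 0.7 (an assumption), a fall of 0.03 to 0.17 log units remains with ρ of 0.5 to 0.8 and GM 2.0. This also stands, and is a further reason to rest conclusions on the between-group difference.

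**Conclusion.** The concern holds. The outcome text and Table 2 conflict on the pre-treatment IL-6 sample, and the analysis section does not resolve it. If Table 2 is followed, each arm's change contains regression to the mean. Its direction follows from selection above a cut-off. Its size depends on the source distribution and the within-person correlation, neither of which the plan gives.

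Under the main assumptions, and with the two-measure entry rule, the spontaneous fall is 7 to 20%, depending on whether the Screening visit 1 value or the average serves as baseline. The false-decrease rate is 6 to 30% on the log scale and 4 to 19% on the raw scale. At a correlation of 0.9 it is much smaller, and on the raw scale can be close to nominal. The between-group difference and the stated power are unaffected. This should be corrected, but it does not threaten the randomised comparison.

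**What to change.** 1. In Table 2, mark IL-6 at the Baseline visit, so that it agrees with item f of Outcome Measures. Reconcile the screening entries with inclusion criterion 4, since a second screening measure is described but not marked.
2. In Statistical Analyses, define the IL-6 baseline as the Baseline-visit sample, and state that a screening value used for eligibility does not serve as baseline.
3. State that the between-group difference in IL-6 change is the primary estimate and that within-group changes are descriptive only. Add the comparison with placebo to Hypothesis 3.

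The cost is one IL-6 assay, in duplicate, per randomised participant: 24 to 30 assays, because the plan gives both 24 participants and 15 + 15. About 60 ml of blood is already drawn at that visit, and item f already intends the assay. The rest is wording. The change should be made before Baseline visits take place, because the plan says nothing about keeping Baseline samples for a later IL-6 assay.
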